4. MILESTONES

Milestone	Estimated date
Draft Protocol Submission to EMA	December 2023
Final Protocol Submission to EMA	April 2024
Registration in the EU PAS register	August 2024
Study Start (after Protocol Approval)	August 2024
CCI	

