5.2. Rationale

The potential benefits of CAB as a new, LA PrEP regimen with superior efficacy as compared to an active comparator taken daily outweigh the potentially low risks of acquiring HIV and subsequent resistance development. There is a risk for HIV acquisition if the individual does not adhere to the CAB PrEP dosing schedule, and protective levels of CAB decrease to a level where HIV acquisition can occur. There may also be risk for HIV acquisition if the individual does not use other HIV-1 prevention strategies, including knowledge of HIV-1 status, regular testing for other sexually transmitted infections, condom use, etc. A warning and precaution are included in product labelling with recommendation that individuals should be counselled periodically to strictly adhere to the recommended CAB dosing schedule and the use of other prevention strategies. There is also a risk for the development of resistance in individuals with unrecognized or acute HIV-1 infection at the time of starting CAB PrEP.

In addition, there is risk of HIV-1 infection during or following CAB PrEP discontinuation, i.e. during the CAB exposure that is detectable >52 weeks post injection (PK tail), and subsequent emergence of CAB resistant HIV-1 strains. A warning and precaution are included in product labelling with recommendation for monitoring to clinically reassess individuals for risk of HIV acquisition and to test to confirm HIV negative status. Although not treatment limiting, CAB LA usage has the risk of hepatotoxicity and potential for HSRs. This 5-year long prospective, non-interventional study will aim to further understand and quantify the risks in real world clinical settings. The additional data generated will continue to inform clinical practice of CAB LA for PrEP usage.

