 - ii. Describe reasons for discontinuation of CAB LA PrEP
 - iii. Describe characteristics of the individuals who discontinue CAB LA PrEP
- 3) Effectiveness: Monitor for incidence of HIV diagnoses while on CAB for PrEP and describe the timing of incident HIV diagnoses with respect to timing of CAB for PrEP usage
 - a. Describe the proportion and number of incident HIV-1 infections while on CAB for PrEP among individuals in the following groups:
 - i. Infected during OLI
 - ii. Infected while on CAB LA: Incident HIV diagnoses, defined as HIV diagnosed after start of CAB injections while adhering to CAB LA PrEP regimen
 - b. Describe the timing of diagnosis of HIV with respect to timing of CAB for PrEP usage among individuals in the following groups:

- i. Infected during OLI
- ii. Infected while on CAB LA: Incident HIV diagnoses while adhering to CAB LA PrEP regimen
- c. Describe the proportion of incident infections among those who start with OLI and those who go to DTI separately and the timing of diagnosis of incident HIV for the overall group, and separately for the OLI and DTI groups.

The proposed study is a non-interventional study and will collect data from routine clinical practice and plans to capture all prevalent HIV-1 infections, including those captured during baseline. However, there are no plans to collect and store serum samples for subsequent testing as this is not part of standard of care.

- 4) Safety: Monitor for occurrence of DILI and HSRs following CAB LA injections
 - a. Describe the frequency of DILI after starting CAB LA at 6, 12, 24, 36, and >36 months after initiation as defined in Section 7.3.2.
 - i. Incidence proportion and rate of DILI following administration of CAB LA PrEP
 - ii. Incidence proportion and rate of CAB LA discontinuation due to DILI
 - b. Describe the frequency of HSR after starting CAB LA at 6, 12, 24, 36, and >36 months after initiation
 - i. Incidence proportion and rate of HSR following administration of CAB LA PrEP
 - ii. Incidence proportion and rate of CAB LA discontinuation due to HSR
- 5) Resistance: Evaluate incidence of and risk for developing resistance to integrase inhibitors (INSTI) among individuals in the following groups:
 - a. Incident HIV diagnoses while adhering to CAB LA for PrEP and development of resistance during treatment for HIV
 - b. CAB LA PrEP discontinued:
 - i. without subsequent oral PrEP & potential risk for HIV acquisition and viral resistance during CAB LA PK tail

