 - ii. switched to oral PrEP and acquire HIV during the remainder of the follow-up period and develop resistance during subsequent treatment with ARVs
 - c. Individuals with undiagnosed prevalent HIV at initiation of CAB PrEP and subsequent emergence of resistance while on CAB monotherapy

Resistance testing: Since this is a non-interventional study aiming to capture standard of care (SoC) in real world settings, the study will not mandate resistance testing following discontinuation of CAB LA for PrEP. Health care providers following the SmPC and applicable local guidelines will decide what laboratory and resistance tests are to be conducted while an individual is on CAB LA for PrEP. Data thus generated, including available HIV-1 subtypes, will be captured

and analysed by the study team. Resistance will also be assessed among the individuals who are non-adherent to the injection regimen and acquire HIV.

7. **RESEARCH METHODS**

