- b) Individuals with undiagnosed prevalent infections at the time of CAB PrEP initiation
- c) Durability of INSTI-based vs. non-INSTI based regimens (e.g., the numbers and proportions of those who achieve and maintain virologic suppression, the time to virologic suppression, the time to virologic breakthrough), as well as any INSTI resistance-associated substitutions that are detected upon ART failure

5) Adherence and Durability

- a) Adherence to CAB LA PrEP including OLI will be estimated from data collected via health record data
- b) Non-adherence to the dosing schedule will be assessed by:
 - Estimating the number of individuals that missed one or more consecutive injections without taking daily oral PrEP bridging while not on CAB LA injections and mean and median number of injections missed during a 6 and a 12-month period
 - Estimating the number of individuals who received the injections seven or more days later than their scheduled injection visit and median duration of delayed injections
 - Estimating the number of individuals who missed one or more consecutive injections without taking daily oral PrEP bridging or those who received the injections seven or more days later than their scheduled injection visit (Combined group a OR b) and describe characteristics for the individuals that are nonadherent
- c) Discontinuation will be defined as 2 injection cycles (~127 consecutive days) in which no injections were administered without oral PrEP bridging
- d) Describe the frequency and the regimen used for oral PrEP bridging to cover planned delayed or missed injections
- 6) Frequency of resistance to INSTIs and specific mutations among the following groups:
 - a) CAB LA PrEP started when the individual had undiagnosed HIV and subsequent emergence of resistance while on CAB monotherapy
 - b) CAB LA PrEP discontinued
 - without subsequent oral PrEP & potential risk of HIV acquistion and viral resistance during CAB LA PK tail
 - switched to oral PrEP and acquire HIV during the follow-up period and develop resistance during subsequent follow-up period while on treatment with ARVs
 - c) Incident HIV diagnosis while adhering to CAB LA for PrEP and development of resistance during treatment for HIV
- 7) Frequency of DILI and HSRs following CAB OLI and CAB LA injections assessed at 6, 12, 24, 36, and >36 months.

Hepatotoxicity related to administration of CAB for PrEP (i.e., DILI) as described below will be tabulated:

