DILI case definition: Determination of suspected or potential DILI will be based on liver chemistry criteria (ALT, BILI and ALP) in addition to all relevant clinical information based on Aithal et al, 2011.⁵ An independent adjudication committee will review all potential and suspected cases of DILI that meet the liver chemistry criteria for DILI for drug attribution to CAB for PrEP. The adjudication committee will be provided with all relevant clinical information collected from data in the health records, to enable a comprehensive review and assessment of potential DILI attributed to CAB PrEP.

Liver chemistry criteria for DILI including any one of the following:

- a) More than or equal to fivefold elevation above the upper limit of normal (ULN) for ALT
- b) More than or equal to twofold elevation above the ULN for ALP (particularly with accompanying elevations in concentrations of 5'nucleotidase or γ-glutamyl transpeptidase in the absence of known bone pathology driving the rise in ALP level)
- c) More than or equal to threefold elevation in ALT concentration and simultaneous (within +/- 2 weeks) elevation of BILI concentration exceeding 2× ULN after starting CAB LA PrEP at 6, 12, 24, 36, and >36 months after initiation

If the person has had previous liver injury and hence abnormal LCT prior to starting CAB for PrEP, ULN is replaced by the mean baseline values obtained at baseline, (i.e., 5× baseline for ALT, 2x baseline for ALP and 2× baseline for BILI with associated 3× baseline elevation in ALT). Classification of the clinical severity of DILI involves use of the peak measured values for each of the biochemical parameters during the course of DILI.

Cases of suspected or potential DILI with attribution to CAB for PrEP will be tabulated according to the DILI severity grade as below:

Description of HSR: Signs and symptoms of HSR reported with INSTIs include, but are not limited to, severe rash, or rash accompanied by fever, general malaise, fatigue, muscle or joint aches, blisters, oral lesions, conjunctivitis, facial oedema, hepatitis, eosinophilia or angioedema. Clinical status, including liver transaminases, will be considered and frequency of HSRs will be assessed at 6, 12, 24, 36, and >36 months after study start.

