ART regimen and VL testing among CAB PrEP users with undiagnosed prevalent infections and incident infections will be described separately, during the follow-up period. In the event of a delay of ART initiation post HIV diagnosis, the study will strive to follow the individual after ART initiation and through the end of the follow-up period. Durability of INSTI-based vs. non-INSTI based regimens (e.g., the numbers and proportions of those who achieve and maintain virologic suppression, the time to virologic breakthrough), as well as any INSTI resistance-associated substitutions that are detected upon ART failure will also be assessed and reported.

Analysis for Objective 4 (Safety: Monitor for occurrence of DILI and HSR)

Proportion and number of individuals with DILI and HSRs following CAB OLI and CAB LA injections will be shown separately at 6, 12, 24, 36 months after initiation and over the entire length of the follow-up period. Proportion and number of individuals discontinuing CAB OLI and CAB LA PrEP due to DILI or HSR will be shown at 6, 12, 24, 36 months and over the entire length of the follow-up period. Discontinuation of CAB LA PrEP or CAB OLI will be based on medical records indicating date when discontinuation decision was made by a physician and will be reviewed and confirmed by an independent adjudication committee. Frequency of hepatotoxicity and HSR events will be reported separately for OLI period and during injections.

Analysis for Objective 5 (Resistance monitoring)

Proportion and number of individuals developing drug resistance to INSTIs based on genotypic data will be assessed among the 4 different groups as follows:

a) Individuals with undiagnosed prevalent HIV, initiating CAB OLI or CAB LA PrEP, will be followed through the end of the follow-up period after ART initiation and will be monitored for resistance

- b) Individuals with incident HIV while on CAB LA PrEP will be followed through the end of the follow-up period following ART initiation and monitored for resistance
- c) Individuals who discontinue CAB LA PrEP will be followed through the end of the follow-up period and if they acquire HIV will continue to be followed after ART initiation to monitor for resistance
- d) Individuals who switch to oral PrEP and acquire HIV during the 12- month follow-up period while on oral PrEP will be followed through the end of the follow-up period after ART initiation and monitored for resistance

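### Two time windows contradict the objectives: Section 7.3.2 counts HSR from study start rather than CAB initiation, and Section 7.6.1 group (d) limits HIV after a switch to oral PrEP to an undefined 12 months

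*Protocol*

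**What the plan says.** **HSR clock.** Section 7.3.2, in the HSR text under outcome 7, states in two consecutive paragraphs that "frequency of HSRs will be assessed at 6, 12, 24, 36, and >36 months after study start". Section 6, Objective 4(b), reads "Describe the frequency of HSR after starting CAB LA at 6, 12, 24, 36, and >36 months after initiation". The Objective 4 analysis in Section 7.6.1 says that DILI and HSR results "will be shown separately at 6, 12, 24, 36 months after initiation and over the entire length of the follow-up period". DILI is counted after initiation in Section 6, in the liver chemistry criteria of Section 7.3.2 and in Section 7.6.1. Section 4 lists "Study Start (after Protocol Approval" among the milestones, with an estimated date of August 2024.

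**Switch to oral PrEP.** Section 6, Objective 5(b)(ii), concerns people who "switched to oral PrEP and acquire HIV during the remainder of the follow-up period". Outcome 6(b) in Section 7.3.2 has "switched to oral PrEP and acquire HIV during the follow-up period". Section 7.6.1, Objective 5 group (d), has "Individuals who switch to oral PrEP and acquire HIV during the 12- month follow-up period while on oral PrEP". Sections 7.1 and 7.5 and the opening of Section 7.6.1 all follow people who stop CAB LA to the end of the follow-up period.

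**The concern.** Both are conflicts between rules that the protocol fixes itself, so they are not details left for an analysis plan.

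For HSR, months since a calendar date and months since a person's first exposure are different quantities once entry is staggered. A proportion taken 6 months after study start is not a 6-month risk on drug. It pools people who began at different times, and it puts one of the two adjudicated safety outcomes on a different clock from the other.

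For switchers, group (d) as written does not answer Objective 5(b)(ii). An infection after the twelfth month falls outside the group that the objective asks about, although the person is still being followed. The start of the 12 months is not given either: it could be the switch, CAB initiation or study start. Few HIV cases are to be expected in a cohort of about 500, so one or two placed in the wrong row would change a group's resistance proportion.

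**Working it through.** **1. HSR: the texts side by side**

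| Place | Months counted from |
|---|---|
| Section 6, Objective 4(b) | CAB LA initiation |
| Section 7.3.2, HSR text (two sentences) | study start |
| Section 7.3.2, DILI criteria | initiation |
| Section 7.6.1, Objective 4 analysis (DILI and HSR) | initiation |

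The odd ones out are the two HSR sentences in Section 7.3.2.

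**2. HSR: how far apart the clocks are**

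Inputs from the protocol: follow-up ends five years after first enrolment (Section 7.2.1), each user is followed for at least 3 years (Section 7.1), and the target is at least 500 (Section 7.4.1). If both durations hold, entry lasts at most 60 − 36 = 24 months. The accrual length is not stated.

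Assumptions: uniform accrual over A = 12 to 24 months, no dropout, N = 500, and study start taken as the date of first enrolment.

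At t months after study start:
- share enrolled = min(t/A, 1)
- mean exposure among those enrolled = t/2 if t ≤ A, otherwise t − A/2
- person-months, study-start clock = 500 × share enrolled × mean exposure
- person-months, initiation clock = 500 × t

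For t = 6 and A = 24: 500 × 0.25 × 3 = 375, against 500 × 6 = 3000, or 12.5%. For t = 6 and A = 12: 500 × 0.5 × 3 = 750, or 25%.

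| t (months) | Initiation clock | Study start, A = 24 | Study start, A = 12 |
|---|---|---|---|
| 6 | 3000 | 375 (12.5%) | 750 (25%) |
| 12 | 6000 | 1500 (25%) | 3000 (50%) |
| 24 | 12000 | 6000 (50%) | 9000 (75%) |
| 36 | 18000 | 12000 (67%) | 15000 (83%) |

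These are ratios of person-time. They are not estimates of bias in an HSR proportion or rate. They show that the two readings describe different exposure, most of all at the early time points: those enrolled by 6 months after study start have been exposed for 3 months on average.

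**3. Switchers: the texts side by side**

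| Place | Window for HIV acquisition |
|---|---|
| Section 6, Objective 5(b)(ii) | rest of follow-up |
| Section 7.3.2, outcome 6(b) | follow-up period, no limit in months |
| Section 7.6.1, group (c), all who discontinue | end of follow-up |
| Section 7.6.1, group (d), switchers | 12 months, origin not stated |

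No 12-month follow-up period is defined elsewhere in the protocol. The limit in group (d) applies to acquisition only: once HIV is acquired, resistance is followed to the end of the study.

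The protocol gives no figure for either window that could be reproduced.

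**The case against.** **HSR.** The analysis section, which governs the tables, already has the right clock and agrees with the objective. The slip is one sentence that appears twice, so a wrong analysis is not the likeliest outcome. That stands, and it limits the seriousness. It does not remove the conflict, because the outcome definition is a natural place for a programmer to look. Study start could also be read as each person's own entry, but this fits poorly with the dated milestone in Section 4 and with the interim results in Section 7.6.1, which are timed from study initiation.

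A reader might infer that the 6-month HSR figure would mainly describe people who are not yet enrolled. It would not: they contribute neither events nor denominator. Nothing in the protocol puts all 500 in the denominator before they enter.

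**Switchers.** A reader might infer that later infections are lost. The protocol does not support that. Section 6 lists switchers under discontinuation, and group (c) follows people who discontinue without a 12-month limit. Some doubt remains because discontinuation in Section 7.3.2 is defined by about 127 days without injections and without oral bridging, so a person who goes straight to oral PrEP may not meet it.

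It is also tempting to say that the limit cuts into the period in which CAB is "detectable >52 weeks post injection (PK tail". The objective and the outcome definition tie that tail to people who stop without subsequent oral PrEP, not to switchers, and the 12 months have no stated origin.

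A large share can be computed for what falls outside group (d). With entry uniform over 24 months, switching uniform over months 0 to 36, the 12 months counted from the switch, a constant rate and no loss, mean time after the switch is 60 − 12 − 18 = 30 months. About 39% of it lies in the first 12 months, which leaves 61% outside. In cases this is small. If 2.5% to 20% of 500 switched (the range of Table 2, used as a stand-in) at 1.22 per 100 person-years (Section 5.1, the TDF/FTC arm of HPTN 083), infections number 12.5 × 2.5 × 0.0122 ≈ 0.4 to 100 × 2.5 × 0.0122 ≈ 3. About 0.2 to 1.9 of these would come after month 12. The assumptions are too many for 61% to serve as the size of the problem.

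**Conclusion.** Both contradictions are in the current text and should be corrected. They are errors of consistency, limited in reach, and do not undermine the study design.

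For HSR, Section 7.3.2 conflicts with the objective, with the analysis section and with the handling of DILI. If it were followed, results at each time point would mix people with different exposure and could not be compared with the DILI results. The size depends on accrual. Under the uniform 12- to 24-month assumption, the study-start clock holds a quarter to an eighth of the initiation-clock person-time at 6 months, and a half to a quarter at 12 months.

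For switchers, group (d) contradicts Objective 5(b)(ii) and outcome 6(b) through a window that has no origin and no definition. Later infections may appear under group (c), but group (d) would omit them, which distorts the resistance results for those who switched against those who did not. The protocol allows no firm figure for how many cases this affects, and the number is likely to be small.

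**What to change.** Three wording edits:

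1. In both HSR sentences of Section 7.3.2, replace the reference to study start with months after CAB initiation. Count from the first CAB LA injection for the injection period and from the first OLI prescription for the OLI period. A single origin would clash with Objective 4(b), which starts at CAB LA, and with Section 7.6.1, which reports the OLI and injection periods separately.
2. In Section 7.6.1, Objective 5 group (d), replace the 12-month window with that of Objective 5(b)(ii), that is, the remainder of the follow-up period.

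Item 1 is two edits and item 2 is one. No new data are needed: Section 7.5 already provides for injection dates and for follow-up after discontinuation. The cost is a short protocol amendment, best made before the first interim results at 12 months.

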7.3.3. Confounders and effect modifiers

The study will examine the effect of the following potential confounders and effect modifiers on the risk for outcomes of interest. These variables will be measured at baseline and at 6, 12, 24, 36, and >36 months as available.

Demographic Variables

- Age at index date
- Sex and Gender
- Ethnic Origin
- Geographic region (where provided)

Clinical Characteristics

- Substance use
- Alcohol use
- Charlson Comorbidity Index (CCI)
- Body Mass Index (BMI), weight, height
- High risk sexual behaviour
- STI testing in the past 12 months
- STI diagnoses in the past 12 months (chlamydia, syphilis, gonorrhoea, and other STIs combined)
- Cardiovascular
 - Hypertension as >130 mmHg systolic, >=90 mmHg diastolic,
 - \circ Triglycerides >=1.5 g/l
 - LDL > 100 mg/dL, Index of Total Cholesterol/HDL Cholesterol
 - ASCVD risk >7.5%
 - CVD incidence
- Hepatic: the following liver chemistry tests (LCT) data will be collected when tested for:
 - Alanine aminotransferase (ALT) elevations (also called serum glutamic pyruvic transaminase (SGPT))
 - Aspartate aminotransferase (AST) elevations (also called serum glutamic oxaloacetic transaminase (SGOT))
 - Total bilirubin elevations (BILI)
 - Alkaline phosphatase (ALP) elevations where available
 - o Albumin
 - Prothrombin time (PT) where available
 - Lipase levels where available
 - o Fib-4
- Hepatitis C and hepatitis B incidence and chronic infection
- Use of recreational drugs (cocaine, narcotics, psychodysleptics [hallucinogens], psychoactive substance, antiepileptic, sedativehypnotic and anti-parkinsonism drugs)

History of PrEP use

- Current or any prior daily PrEP use (yes, no)Time and duration on prior daily PrEP use:<2 months
 - \circ 2-6 months
 - \circ 6-12 months
 - \circ 12+ months
- Number of months on PrEP in the last 12 months (mean and median)
- Type of daily PrEP used (TDF, TAF)
- Use of CAB oral lead in prior to initiating injections

7.4. Data sources

Data will be collected from participating European clinical sites within the NEAT-ID Network. Selected sites will be contacted and asked to identify individuals initiating CAB LA for PrEP. The NEAT-ID Network coordinating center will receive data from the clinical sites for the study; data will be extracted from medical records to capture the study variables relevant to the study objectives, as listed in Section 7.3 Variables. Data will be entered into the EDC system from each site. All data will be deidentified and electronically transferred to the coordinating center. Sites will be regularly monitored for data quality and accuracy.

